7.3.2 Muscle Strength Testing

7.3.2 (i) Tibialis Anterior Strength

With the participant positioned in supine on a bed or plinth, with hip and knee at 0 degrees if possible. The thigh is fixed by the participants parent or a strap; to stop the knee bending and the handheld dynamometer is placed just proximal to the metatarsophalangeal joint on the dorsum of the foot [19]. The participant positions their foot in plantigrade (90° at the ankle) and is then asked to lift their foot upwards and the maximal force will be recorded, if the child is unable to achieve ankle plantigrade a score of 0 is given [19]. Three measures will be taken of each leg and the maximal reading used, normalised to body weight.

7.3.2 (ii) Quadriceps strength

The participant will be positioned in sitting, back supported by a chair, the knee is firstly positioned by the SC at 30 degrees flexion using a goniometer and rested on a stand (see figure 3) [19-21]. A handheld dynamometer will then be placed on the distal tibia and the participant will be asked to push their leg straight [19-21]. The maximal force will be recorded. The test is repeated with the knee at 90 degrees. For each test three measures will be taken of each leg and the maximal reading used, normalised to body weight and the same adjustable chair will be used for each participant to standardise the measurement.

Health Research Authority

Figure 3: Position of the CYP for handheld dynamometer testing of quadricep strength.

7.3.3 Foot Posture

Foot posture will be established with the CYP in standing and barefoot. Hind foot position whilst weight bearing and the presences of a midfoot break will be recorded using the CPIP manual as a guide [17] A review of Foot posture will only take place at the initial baseline assessment 'usual' care, so that its effect as predictor on outcomes can be examined .

7.3.4 GOAL Questionnaire

The GOAL questionnaire will be issued to both Parent and Child. The GOAL consists of 48 items grouped into seven domains; domain A: activities of daily living and independence; domain B: gait function and mobility; domain C: pain, discomfort and fatigue; domain D: physical activities, sports and recreation; domain E: gait pattern and appearance; domain F: use of braces and mobility aids; domain G: body image and self-esteem and takes approximately 10 minutes to complete [22].

7.3.5 Walking Assessment

The walking assessment will take place across a 5-metre level walkway either in the child's home, local clinic room or University lab. The same setting will be used for each walking assessment pre and post usual physiotherapy and FES intervention. An electric goniometer will be placed over the knee joint (see figure 4) to measure the degree of knee flexion at initial contact and midstance in the most affected leg. An additional electrogoniometer will record ankle dorsi-/plantar-flexion and an accelerometer placed on the tibia to aid in the detection of initial contact while walking. Signals are sent via Bluetooth to a recording unit (Biometrics, DataLITE, UK) and analogue signal outputs are AD converted using a 1401 (CED electronics, Cambridge, UK) and recorded using Spike 2 software (version 6 CED electronics, UK).

To calibrate the electrogoniometer the output signal will be recorded while the participant is supine or sitting and the knee is passively positioned to 0 degrees and 90 degrees respectively (as confirmed using a manual goniometer). The most affected leg will be established through assessment of muscle length, spasticity and strength, taken during measures of impairment. At the pre 'Usual' physiotherapy care baseline assessment (Week 0) and the post 'Usual' physio care assessment (week 8) the CYP will be asked to complete an extensive walking assessment in the following three conditions 1.wearing their AFO's (if present) and normal footwear, 2. wearing their AFO and the FES pocket box (FES turned off and not connected to either lower limb muscle group), 3. Wearing No AFO (if safe to do so) and the FES pocket box (turned off and not connected to either lower limb muscle group), with each three conditions repeated three times (see figure 5A). In the pre 'FES' intervention and post 'FES' intervention assessment the CYP will be asked to complete the walking assessment in the following three conditions. 1. Wearing normal footwear and AFO, 2.FES ON and wearing normal footwear, 3. FES Turned off and wearing normal footwear, with each condition repeated three times. (see figure 5B).

Figure 4. Electric goniometer placement for walking and stairs assessment

7.3.6 Stairs Assessment

[figure not shown]
For the stairs assessment the CYP will be asked to walk up and down a flight of stairs using their preferred method, but not exceeding one step at a time as carried out in a similar FES case study on children with CP [12]. If the baseline assessment is being carried out at the participants home this will be on their flight of stairs, alternatively this may be stairs at a local clinic or the university if this is a preferred location for the CYP and family to have their baseline assessments, but the flight of

Health Research Authority

stairs will remain the same for each individual participant for the duration of the study. During the stairs assessment the child will wear and electric goniometer over the knee joint (see figure 4) to record the degree of knee flexion. A video recording of the child ascending a descending the stairs will be taken and a tick box form will be used for the SC to describe their technique and the stairs being used (see appendix 6). The stairs assessment will be carried out pre – 'Usual' physiotherapy (week 0) with AFO's/Orthotics and again post 'Usual care' (week 8). It will then be repeated pre-FES intervention (week 10) and post- FES intervention, with AFO's/Orthotics and with FES On and normal footwear and FES OFF and normal footwear (See figure 5)

Figure 5: A) Diagram of the walk and stairs conditions during 'Usual' physiotherapy care.

B) Diagram of the walk and stairs conditions during the FES intervention

Health Research Authority

7.3.7 Selective Motor Control (SMC)

SMC will be assessed using the validated, Selective Control Assessment of the Lower Extremity (SCALE) tool [3]. This tool was developed by Fowler *et al.* (2009) for health professionals to clinically assess SMC in the entire lower limb in patients with spastic CP. The SCALE assessment will be completed by the SC with participants positioned in sitting, except for the assessment of the hip, which will be performed in side-lying. The assessment will be filmed using 2 static cameras set up to give a lateral and frontal view and the video footage will be used by the SC to calculate the SCALE score for each participant's lower limb. The SCALE will take place at the baseline assessment on Week 0, post usual care assessment (week 8), pre FES intervention assessment (week 10) and post FES intervention (Week 19) (see figure 1)

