7.3.1 Passive Range of Motion (PROM) and Modified Tardieu Scale (MTS)

7.3.1 (I) Popliteal Angle and Hamstring Spasticity

The popliteal angle (assessment of hamstring length) will be obtained from both lower limbs with the participant positioned in supine lying on the plinth. The SC will flex the participants hip to 90 degrees and extend the knee, the research assistant will then record the popliteal angle using a goniometer, in accordance with Cerebral Palsy Integrated Pathway (CPIP) measurement guidelines [17]. This will then be repeated 3 times on each leg (see figure 3 A).

To establish hamstring spasticity this same movement will then be repeated on each leg at a fast speed termed R1, in the Modified Tardieu Scale (MTS) [18]. When the examiner feels a 'catch' during the movement a goniometer measurement will be taken to establish the spasticity component within the hamstrings muscle (see CPIP measurement guidelines [17])

A B

Figure 2 A Measurement of popliteal angle B Measurement of ankle angle

7.3.1 (II) Passive Ankle Range of Motion and Gastrocnemius spasticity

The participant will be positioned in supine on a plinth. The SC will extend the knee and dorsiflex the ankle (assessment of Gastrocnemius length), whilst the research assistant measures the degree of ankle dorsiflexion. This will then be repeated with the knee flexed (assessment of soleus length). Both goniometer measurements will

be repeated 3 times, so that an average measure of gastrocnemius and soleus length is obtained for each lower limb (see figure 2B and CPIP manual [17]).

To establish gastrocnemius spasticity, the ankle, with the knee extended will be dorsiflexed quickly, where a catch is felt (R1) and measure of gastrocnemius spasticity will be taken using the goniometer. This will be repeated once on both ankles in accordance to the CPIP manual [17]

7.3.1 (III) Duncan Ely and Rectus Femoris spasticity

To establish passive rectus femoris muscle length the child will be positioned prone, the knee will be flexed slowly and the heel brought towards the child's bottom, the goniometer is placed over the child's knee and a measure of this range of motion is taken. This will be carried out in accordance to the CPIP manual [17] and the measure will be repeated three times on each lower limb.

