10.1 FES Set Up (week 9)

Once a decision is made about the muscle group being stimulated by FES the participant will be set up with an Odstock Dropped Foot Stimulator ODFS® Pace or if the participant prefers, the wireless version ODFS® Pace XL FES device. FES set will take place in week 9 with the SC at the participant preferred location (see figure 1). For Tibialis anterior stimulation, FES set up will take place with the participant in sitting. The SC will place two, 50mm x 50mm PALS Plus® square electrode pads (see figure 6A) on the lower leg, one over the head of the fibula and the other over the muscle belly of Tibialis Anterior, in accordance to the ODFS® Pace and ODFS® Pace XL manual (see figure 6B). In participants with smaller legs, the electrodes may need to be cut down to size for an accurate muscle stimulation. The SC will then turn up the FES current until a contraction is observed in the muscle and the foot begins to dorsiflex and evert.

В

Figure 6: A PALS® Plus square electrode 50mm x 50mm B FES electrode placement for Tibialis
Anterior stimulation

If the participant is being set up with FES to stimulate the quadriceps the SC will place two PALS Plus® round electrodes of either size 25mm or 32 mm (depending on the size of the child's leg) over the distal vastus medialis oblique and proximal lateralis, in accordance to the manual (see figure 7B). With the participant sat up on a bed and the knee straight, the SC will gradually increase the FES current until a contraction is observed in the quadricep muscle belly.

Figure 7: **A** PALS round electrodes

B FES electrode placement for quadricep stimulation

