	Once the child is walking with the FES the SC may have to make further adjustments to the timing and speed of the muscle activation for optimal gait performance. Following FES training the CYP will be asked to use the FES daily, this should start in and around the house, but building up confidence to wearing it in the community setting or at school. The aim is to build up to wearing the FES for between 2-4hours a day in preparation for starting the FES intervention phase of the study at week 11. One week after receiving FES training (Week 10), the participant will receive a home visit from the physiotherapist to check the CYP has been using it correctly and to make any changes required to optimise gait.
5. WHO PRIVIDED for each	The initial screening, physical screening and training home visits will all be provided by the Study Co-
category of intervention provider (e.g. psychologist,	ordinator (SC). The SC is trained Childrens Physiotherapist with over 8 years of experience working with
nursing assistant), describe	children with CP. She completed the OML® FES training course for the lower limb in 2019 and uses FES
their expertise, background and any specific training given	regularly for the treatment of drop foot in CYP with CP at Torbay Hospital CDC
6. HOW. describe the modes	The initial screening for study eligibility will take place over a telephone conversation. FES set up and
of delivery (e.g. face-to-face or by some other mechanism, such as internet or telephone) of the intervention and whether it was provided individually or in a group	training will take place face to face.
7. WHERE: describe the	FES set up and training will take place in the CYP home or at a preferred location such as the University of
type(s) of location(s) where the intervention occurred,	Plymouth Human Movement and Function Lab or in a clinic space situated with the child's NHS Trust
including any necessary infrastructure or relevant features.	Providers CDC.
8. WHEN AND HOW MUCH	Each CYP will be asked to use the FES device for between 2-4 hours a day, 6 days a week. This duration
describe the number of times the intervention was delivered and over what period including	has been guided by PPI feedback on the study protocol and a RCT on the use of FES in drop foot in

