the number of sessions, their schedule, and their duration, intensity, or dose	children with CP [26]. The FES can be worn at home and or at school depending on the preferences of the CYP. The CYP will be asked to avoid starting any new physical activities or sports during the period of FES intervention but may continue with their usual physiotherapy routine
9. TAILORING if the intervention was planned to be personalised, titrated, or adapted, then describe what, why, when, and how.	The FES intervention including the frequency, pulse width and amplitude is tailored to the individual. It will be based on the clinical judgement of the SC, in accordance to the CYP muscle response to stimulation and in order to optimise gait performance. FES electrode pad placement for both Tibialis Anterior and Quadriceps may differ between individuals due to variations in anatomy, but electrode placement will remain the same for a CYP throughout the study.
10. MODIFICATIONS if the intervention was modified during the course of the study, describe the changes (what, why, when, and how).	Modification to the FES intervention may occur if the child has an adverse skin reaction or if they are finding it difficult to tolerate the FES stimulation
11. HOW WELL if the intervention was modified during the course of the study, describe the changes (what, why, when, and how).	To be explored post FES Intervention

NHS

Health Research Authority

References

- [1] P. Rosenbaum, N. Paneth, A. Leviton, M. Goldstein, and M. Bax, "A report: The definition and classification of cerebral palsy April 2006," in *Developmental Medicine and Child Neurology* vol. 49, ed, 2007, pp. 8-14.
- [2] M. Noorkoiv et al., "Predictors of Walking Efficiency in Children With Cerebral Palsy: Lower-Body Joint Angles, Moments, and Power," Physical Therapy, vol. 99, no. 6, pp. 711-720, 2019, doi: 10.1093/ptj/pzz041.
- [3] E. G. Fowler, L. A. Staudt, M. B. Greenberg, and W. L. Oppenheim, "Selective Control Assessment of the Lower Extremity (SCALE): development, validation, and interrater reliability of a clinical tool for patients with cerebral palsy," *Developmental Medicine & Child Neurology*, vol. 51, no. 8, pp. 607-614, 2009/08/01 2009, doi: https://doi.org/10.1111/j.1469-8749.2008.03186.x.

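### SCALE is scored from video by the co-ordinator who delivers FES, with no step to hide the study week; coded, random-order scoring would reduce this risk at little cost

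*Protocol*

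**What the plan says.** On the SCALE itself, Protocol 7.3.7 fixes who conducts it, how it is recorded and who scores it:

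- Conduct: "The SCALE assessment will be completed by the SC with participants positioned in sitting", with the hip tested in side-lying.
- Recording: "The assessment will be filmed using 2 static cameras set up to give a lateral and frontal view".
- Scoring: "the video footage will be used by the SC to calculate the SCALE score".
- Timing: weeks 0, 8, 10 and 19.

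On the intervention, section 10.1 states that "FES set will take place in week 9 with the SC at the participant preferred location". Appendix 8, on tailoring of frequency, pulse width and amplitude, says "It will be based on the clinical judgement of the SC", and it also gives screening and training visits to the SC. Sections 8 and 9 have the SC make the weekly visits. The section on pre- and post-FES assessment has the SC do both the week 10 and the week 19 assessments.

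Section 13.3.2 lists SCALE as a secondary outcome. Section 15.1 has the measures taken at four points summarised by median, range and inter-quartile range, and plotted. No section describes coding of recordings, random-order scoring, a masked rater or a second reading.

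**The concern.** SCALE is a clinician's rating of observed movement, not an instrument reading. The person giving the rating has set up, adjusted and followed the treatment, and has filmed the session, so is in a position to know which phase each recording belongs to. The expected direction is also written down: the rationale in section 2 argues that FES may compensate for impaired selective motor control.

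In an AB design there is no concurrent group in which the same expectation would act and cancel. A more lenient reading at week 19 than at week 10 would appear as a treatment effect. With four points per child, shown descriptively, the planned summary could neither detect nor correct it. Selective motor control is named in objective 3.2, and the study is meant to inform a randomised trial, so the SCALE result may be used later.

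**Working it through.** The protocol gives no figure to reproduce for this point. The check sets the roles side by side, traces how a scoring shift enters the result, and sizes the workload of a remedy.

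**1. Roles**

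| Task | Who | Where |
|---|---|---|
| FES set-up and adjustment | SC | 10.1 |
| Tailoring of stimulation | SC | Appendix 8 |
| Weekly visits | SC | 8, 9 |
| Week 10 and week 19 assessments | SC | Pre and Post FES assessment |
| Conducting SCALE | SC | 7.3.7 |
| Scoring SCALE from video | SC | 7.3.7 |
| Hiding the week at scoring | nobody named | no section |

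**2. How a shift enters the result**

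For one child, write the recorded score at week t as T(t) + c(t) + b(t). T is the true score, c is any effect of how the test was conducted (instruction, encouragement), and b is any expectation effect at scoring. Then:

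reported change = [T(19) − T(10)] + [c(19) − c(10)] + [b(19) − b(10)]

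- A constant leniency gives b(19) = b(10) and cancels. Only leniency that differs by phase matters.
- If b(10) = 0, the change is displaced by exactly b(19). This is true of any additive shift and says nothing about its likely size. The protocol contains nothing from which b could be estimated.
- Hiding the week at scoring acts on the b term only. The c term is already on the film.

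**3. Workload of hiding the week**

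- Participants: 12 (15.3). SCALE sessions per participant: 4 (7.3.7).
- Sessions: 12 x 4 = 48 at most, fewer if children withdraw.
- Files, if each of the 2 cameras gives one file: 48 x 2 = 96.
- Scoring time is not stated. Assuming 10 to 30 minutes per session: 48 x 10 / 60 = 8 hours to 48 x 30 / 60 = 24 hours. Those hours are already implied by scoring from video, so the added work is the renaming and the random list.

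**The case against.** The strongest reply is that nothing here is wrong or contradictory. Section 7.3.7 names the scorer and the medium; it does not say when clips are scored, in what order or how files are labelled. Coded scoring would be compatible with the text as it stands. Knowledge of the phase is an inference from the SC's roles, not a stated rule. SCALE is also one of many secondary outcomes in an exploratory series of 12 children, with no test or decision rule attached. All of this stands and limits the weight of the point. It does not remove it: who scores an outcome, and what they know when scoring, is study conduct, and the protocol has fixed the first without addressing the second.

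A second reply is that the remedy is weak when the SC remains the rater. The SC ran every session, sees the child about 20 times and may recognise a visit from memory. This also stands.

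Three stronger readings are tempting, and the documents do not support them:

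- A reader might infer that shuffling makes an expectation effect cancel over time points. That would need the masking to work fully, which cannot be assumed here.
- A reader might infer that, because the test is done sitting or side-lying, the film cannot show the phase. Children are asked to wear shorts (7.2), electrodes sit on the thigh or lower leg (10.1), walking with FES on belongs to the week 10 and 19 assessments (7.3.5), and section 17.1 anticipates skin marks from the pads. The order of tests is not given, so visible cues cannot be excluded.
- A reader might infer that an immediate SCALE score is needed to choose the muscle. Section 10 says only that baseline outcomes and the Appendix 7 tool guide that choice, and the content of the tool is not shown.

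Nor can it be assumed that a research assistant is available for coding. The role is documented for range-of-motion measurement, as in "the research assistant will then record the popliteal angle using a goniometer", and not for SCALE.

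**Conclusion.** The point holds as an inexpensive improvement. The SC delivers the treatment, conducts SCALE and scores it, with no step to hide the week. In an uncontrolled AB comparison, any phase-dependent leniency enters the week 10 to 19 change in full. Its size is unknown and no figure should be put on it. It would be going too far to conclude that the SCALE results will be biased, or that the primary result is at risk: the primary outcome in 13.3.1 is an electrogoniometer angle and does not depend on this rating.

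The conclusion rests on two assumptions: that SCALE scoring leaves room for judgement, and that, with no masking step written down, the SC would score knowing the week. Coded, random-order scoring would reduce bias at scoring. It would not remove it, and would leave untouched any bias in how the test was conducted.

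**What to change.** Add to section 7.3.7:

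- The SCALE score used for analysis is given from recordings under coded file names that carry no date or week, presented in random order.
- Preferably the recordings are pooled across children and scored in one batch after the last week 19 visit, at most 48 sessions.
- Available recordings of children who withdraw are included where their data may be used under section 12.6.
- The codes and the random list are produced by a script or by a team member other than the SC. The key is opened only after the scores are locked.
- Where the order of tests allows, SCALE is filmed before electrodes are applied that day.
- The report states as a limitation that the rater conducted the sessions, so masking was partial.

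Cost: renaming of files and a random list, with no extra visit or measurement. Scores become available later, and the recordings must be held until the batch is done. If resources allow, a trained rater with no part in FES delivery, scoring the same coded files, would mask better. On the assumed 10 to 30 minutes per session this takes 8 to 24 hours of that person's time.

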8. USUAL PHYSIOTHERAPY CARE

Once the baseline assessment has been completed (Week 0) the child is asked by the SC to continue with their 'Usual' Physiotherapy care. During this time, they are asked to avoid starting any new sports or joining a new physical activity club, but instead to continue with their usual physical activity routine. This 'Usual' care period will last for a duration of 8 weeks (see figure 1). During the usual care period the SC will visit the child once a week in their own home to carry out a weekly physiotherapy assessment

